We will now work on implementing the intervention and assessing changes across interventions with regard to Aims 1-3 outcomes (screening, psychosocial facilitators, network effects). We plan on recruiting 150 Latina women to participate in the Intervention. 75 women will be recruited at The Resurrection Project and 75 women will be recruited from Centro Comunitario Juan Diego. No contact information on women who have participated in any previous focus groups or will we re-contact any woman who has already participated in a focus group for future trial. We will only invite new recruits for the intervention. We will be conducting educational classes and workshops at the two participating sites. The Intervention is broken down into 3 sessions at each site across 3 consecutive weeks. Each session will be held with 5-8 recruited participants. We will hold 5 – 9 sessions at each participating site for three consecutive weeks until we reach our target population of 150 Latina women. The variations in the implementation of Phase 3 Intervention will be the Workshops at each site. Besides each site conducting a Breast Cancer Education session at Session 1, TRP will conduct Communication and Volunteerism workshops at Session 1 and 2. Juan Diego will conduct Diet and Physical Activity workshops at Session 1 and 2. Our outcomes will be measured by Surveys assessed during Session 1, Session 3, and six months post-participation in workshops for 20-30 minutes. At the end of Phase 3, participants who have agreed to be contacted again will be contacted by study staff by phone and given the opportunity to learn about preliminary analyses. Participants will be offered information regarding preliminary analyses of the study. They will have the opportunity to decline learning about study results without any negative impact/costs to their relationships with the study sites or UIC. Script for these calls was submitted as part of Amendment #24.

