which women ultimately consent and participate in interventions. Study staff will have no contact information concerning the women who are reached by the peers, Centro Comunitario Juan Diego and The Resurrection Project, unless women contact study staff directly. Peers, Centro Comunitario Juan Diego and The Resurrection Project will not give any contact information to [name] and her team.

Interested women who have received the recruitment flyers, will contact UIC student/staff who will record women's contact information, screen them for eligibility, and obtain scheduling information for the Intervention sessions. We will ask each participant at time of recruitment/enrollment what language they prefer. Three 2-3 hour Workshop Sessions will then be scheduled for three consecutive weeks and held accordingly. For the Phase 3/Intervention, women will be informed that the sessions and workshops will be a "closed" group format. Once a woman agree to participate and enrolled in one of the 3 consecutive sessions, she cannot change or switch to another group's session.

With regard to interventions, once we have at least recruited 6-8 women per session, Centro Comunitario Juan Diego and The Resurrection Project will determine a date and time for use of conference room and fits within recruited women's schedules and begin the scheduling process. Once a date and time has been confirmed, UIC staff [Appendix P], will contact women two days prior to the session/s to remind them and reschedule, as needed. We will hold 5 – 9 sessions at each participating site for three consecutive weeks until we reach the targeted 150 Latina women.

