Six months after participation in Session 3, participants will be asked to complete Survey 3, which will take about 20-30 minutes. Survey 3 will be administered or in person at Centro Comunitario Juan Diego or The Resurrection Project sites. The reminder script has been modified to include scheduling calls, including for Survey 3 as well as the focus groups. Survey 3 will collect information related to information related to volunteerism history, social interactions, breast cancer beliefs (cultural beliefs, perceived risks, norms and social interactions concerning breast cancer) and breast cancer screening since Survey 1. For participants were in Cohort 1 (who completed participation before approved consent addendum), they will be contacted by phone up to 3 times with a script including consent addendum information to be given that information, wherein they can elect to be notified about future studies, if they are interested. If they are not interested, their data will be eliminated from this file. For cohorts 2-15, after the participant completes the final/third survey, her data will be eliminated from this file, if she chooses not to be contacted for future studies. If she chooses to be contacted for future studies, her information name and phone number (nothing else) will be kept and it will be recorded that she has completed participation, but is willing to be contacted in the future. Subsequently, each time she is contacted, this file will be updated to include a summary of the call. During each call, UIC staff will query the woman about her interest in being contacted in the future. If she chooses not to be contacted from future studies, her name and phone number will be eliminated from this contact log. If she chooses to be contacted for future studies, her name and phone number will remain in the contact log. Participants’ contact information will be kept until after participants decide to stop active participation or 5-7 years after the study is completed.

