
With regard to payment, participants will obtain \$80 in total throughout their participation in the trial. After Session 1, they will receive \$10. After Session 2, they will receive \$20. After Session 3, they will receive \$25. After they complete the 20-30 minute Survey 3, six months after participating in Session 3, they will receive \$25.

The materials for the workshops have been provided.

TRP 75 Latina Women	Compensation for Participants	Juan Diego 75 Latina Women
Three 2 Hour educational classes across 3 consecutive weeks	↔	Three 2 Hour educational classes across 3 consecutive weeks

Sessions will be held with 5-8 recruited participants		Sessions will be held with 5-8 recruited participants
These are 'closed' group format (once a woman is enrolled in a particular group, she cannot change to another group and has to complete all 3 sessions).		These are 'closed' group format (once a woman is enrolled in a particular group, she cannot change to another group and has to complete all 3 sessions).
At Session 1, Participants will complete: 1) Informed consent 2) Survey 1; 3) 1 ½ Hour Breast Cancer Education session;	\$10 Cash ↔	At Session 1, Participants will complete: 1) Informed consent 2) Survey 1 3) 1 ½ Hour Breast Cancer Education session;
At Session 2, Participants will complete: 1) 1 ½ Hour Interpersonal Communication workshop.	\$20 Cash ↔	At Session 2, Participants will complete: 1) 1 ½ Hour Diet Educational workshop.
At Session 3, Participants will complete: 1) 1 ½ Hour Volunteerism; workshop 2) Survey 2;	\$25 Cash ↔	At Session 3, Participants will complete: 1) 1 ½ Hour Physical Activity workshop; 2) Survey 2;
Booster Calls one month after Session 3. Every month thereafter for 6 months.		Booster Calls one month after Session 3. Every month thereafter for 6 months.
At 6 months post-participation, participants will complete: 20-30 minute Survey 3	\$25/Cash ↔	At 6 months post-participation, participants will complete: 20-30 minute Survey 3

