9.0 Data Analysis Qualitative

For **Phase 1, 2, 4 and 7**, [name] and her team [Appendix P] will lead content analyses with inductive and deductive approaches[53, 54] in Atlas.ti.[55] She and two UIC students [TBA] will read transcripts and generate codes. We will compare notes, review data, cluster similar ideas into representative themes, and discuss areas of disagreement until consensus is reached. A final codebook will be used for re-analysis. Sample sizes are within the recommended range to meet thematic saturation.[53,54]

Quantitative

For **Phase 3**, our project will include 3 sets of analyses to examine the 3 outcomes – breast cancer screening, psychosocial facilitators (self-efficacy, norms, support, and knowledge), and social network dissemination. All analyses will be conducted in statistical packages (SPSS, SAS, R).

We will use multiple imputation techniques to handle missing data.⁶⁵ Measures will be assessed and included if they have adequate reliability (Cronbach's $\alpha \geq 0.70$). We will first conduct descriptive statistics. We will identify covariates based on theory and bivariate analyses to examine 1) intervention differences in demographic, healthcare, and pre-study factors (e.g., screening history) and 2) the relationship of these factors to each other and outcomes (e.g., screening). We will conduct a multivariable logistic regression to examine study arm differences in guideline-concordant screening six months after participating in interventions. We will conduct sensitivity analyses, using only women 1) with complete medical record data and 2) recruited by Study Site staff. Based on power analyses to estimate the minimal detectable effect of study arm differences among 150 Latinas on screening, $p < .05$, power = .80 and two-tailed tests, we would be able to detect a medium/large effect in a logistic regression (OR = 2.8).

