We will use identical procedures to handle missing data, assess measure reliability, and inform covariate selection for psychosocial facilitators as we did for screening. Next, we will use mixed modeling and will have two levels, with level 2 being participants and level 1 being the repeated surveys at different time points. We will assess within-participant change over time in each outcome (self-efficacy, norms, support, and knowledge) to identify whether it is best modelled as linear versus non-linear (quadratic). Once determined, we will expand models to examine if there are study arm and study arm*time interaction effects in change over time, adjusted for covariates. Sample size for these analyses include 450 level-1 units (survey time points) and 150 level-2 units (participants). Based on power analyses to estimate the minimal detectable effect size of for study arm differences among 150 Latinas across nested surveys concerning psychosocial facilitators (ICC = 0.0-0.5), $p < .05$, power = .80 and two-tailed tests, we would be

able to detect a small/medium effect for a study arm*time interaction effect using mixed modeling.

We will use identical procedures to handle missing data, assess measure reliability, and inform covariate selection for social network data as we did for screening and psychosocial facilitators. We will first conduct network visualization using Egonet.⁷¹ Network composition and density will be estimated from the first five names/alters women list, which has been documented as adequate and beneficial to minimize respondent burden during small field studies, such as this one.⁷² We will next import data into a standard statistical package^{73,74} and will conduct multivariable regressions or mixed modeling, depending on clustering (e.g., peers referred by peers), to examine study arm differences in Phase 3 outcomes. Based on power analyses for study arm differences among 150 Latinas in network outcomes, $p < .05$, power = .80 and two-tailed tests, we would be able to detect a small effect in multivariable linear regression models (Cohen's $f^2 = 0.05$).

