For **Phase 6**, we will have two sets of analyses. For Phase 6a, we will conduct Generalized Estimating Equation models with main effects (Study arm, time) and interaction terms (study arm*time) for all outcomes, except for civic engagement intention, which was not measured at multiple time points. Based on power analyses to estimate the minimal detectable effect size for study arm differences among 100 Latinas (assuming maximum attrition, given current attrition rates) across nested surveys (ICC = 0.0-0.5), $p < .05$, power=0.80, and two-tailed tests, we would be able to detect a medium-sized effect for a study arm*time interaction effect. For civic engagement intention, we will conduct a logistic regression. We will cluster by cohort/group and adjust for demographic covariates in all models. For Phase 6b, we will assess the: 1) number and types of civic engagement and community development activities; 2) number of women who indicate interest; and, 3) number of women who attend. Secondary analyses include: 1)

describing the number and types of barriers to participation; and, 2) characterizing predictors to participation via bivariate regressions.

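### The Aim 1 and Aim 2 models leave out the closed delivery groups, although Phase 6a clusters on them, and no Phase 3 detectable effect states an allowance for them

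*Combined protocol and SAP*

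**What the plan says.** **Delivery.** Section 3.0 states: "Each session will be held with 5-8 recruited participants". Section 6.2 gives a slightly different threshold for scheduling ("once we have at least recruited 6-8 women per session"). Its Phase 3 table describes the format as closed: "once a woman is enrolled in a particular group, she cannot change to another group and has to complete all 3 sessions". Empowerment sessions are run by one community site and education sessions by the other, so every group lies in a single arm.

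**Aim 1** (section 9.0, Quantitative, Phase 3): "We will conduct a multivariable logistic regression to examine study arm differences in guideline-concordant screening six months after participating in interventions". No random effect, robust variance or group covariate is named.

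**Aim 2** (same section): the mixed model "will have two levels, with level 2 being participants and level 1 being the repeated surveys at different time points".

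**Aim 3** (same section): regression or mixed modelling is to be chosen according to clustering. Peer referral is the example given, and the delivery group is not mentioned.

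**Phase 6a** (sections 6.2, 6.4 and 9.0), which uses the T1-T3 surveys of the same trial: "We will cluster by cohort/group and adjust for demographic covariates in all models". That sentence appears only under Phase 6.

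**Detectable effects** (sections 9.0 and 12.1): for 150 women, two-sided 0.05 and 80% power, OR 2.8 for screening; a small/medium arm-by-time effect for Aim 2 (section 9.0 only); and Cohen's f² of 0.05 for network outcomes. The only ICC given for Phase 3, 0.0-0.5, describes repeated surveys within a woman. No group ICC and no control screening rate are stated.

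**The concern.** Women in a closed group share sessions, companions and facilitators for three weeks. Section 2.0 itself expects part of the benefit to come through contact with informed peers. Outcomes within a group may therefore be correlated.

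Arm does not vary within a group, so this correlation bears directly on the arm comparison. A logistic regression that treats 150 women as independent overstates the information in the data: its standard error is too small, its intervals are too narrow and its test rejects too often.

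Aim 2 needs a distinction. A group effect that is constant over time cancels out of the arm-by-time interaction. That test is affected only if *change* is correlated within groups.

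The plan applies a group rule to a secondary analysis of volunteerism but not to its main screening and psychosocial analyses, and gives no reason for the difference.

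**Working it through.** **1. Inputs from the plan.** 75 women per arm; two-sided alpha 0.05; power 0.80; OR 2.8; groups of 5-8; 240 enrolled and about 150 completing (section 5.0).

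**2. Inputs assumed, because the plan does not give them.** Group ICC 0.01, 0.05 or 0.10. Control screening rate 20-60%.

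**3. The plan's own figure.** OR 2.8 cannot be derived from the documents without a control rate. With the pooled two-proportion formula, 75 independent women per arm and 80% power, the detectable OR is 2.77 at a control rate of 20%, 2.56 at 30%, 2.52 at 40%, 2.59 at 50% and 2.79 at 60%. So OR 2.8 fits independent women at about 20% or about 60%. The Aim 3 f² of 0.05 is also an independent-women figure: the exact value at N = 150 is 0.053, and power at 0.05 is 77.7%.

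**4. Group size in the analysis.** If 5-8 is the size at enrolment, completers number 5 × 150/240 = 3.1 to 8 × 150/240 = 5.0 per group. If 5-8 is the analysed size, it stays at 5-8.

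**5. Design effect**, DE = 1 + (m − 1) × ICC. At ICC 0.05:

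| m | DE | SE too small by √DE | Approximate true alpha, 2[1 − Φ(1.96/√DE)] |
|---|---|---|---|
| 3 | 1.10 | 1.05 | 6.2% |
| 5 | 1.20 | 1.10 | 7.4% |
| 8 | 1.35 | 1.16 | 9.2% |

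At ICC 0.10, m = 5 gives DE 1.40 and alpha 9.8%; m = 8 gives DE 1.70 and alpha 13.3%.

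**6. Simulated type I error of the unclustered Aim 1 test** (beta-binomial outcomes, Wald test of the log OR, 75 per arm, 40,000 runs). Ranges cover 20%, 35% and 60% screened:

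| Analysed women per group | ICC 0.01 | ICC 0.05 | ICC 0.10 |
|---|---|---|---|
| 3-5 | 4.9-5.5% | 5.8-7.6% | 6.9-10.3% |
| 5-8 | 5.1-6.1% | 7.2-9.5% | 9.4-13.7% |

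With independent women the same test gives 4.6-5.2%. A cluster-robust test with t on 2K − 2 degrees of freedom (K groups per arm) gives 5.0-5.3% throughout, assuming no site difference.

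**7. Detectable OR and power**, using n = 75/DE per arm:

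| Control rate | Detectable OR at DE 1 / 1.10 / 1.20 / 1.35 | Power at OR 2.8, same DEs |
|---|---|---|
| 20% | 2.77 / 2.90 / 3.03 / 3.22 | 81.0 / 77.1 / 73.4 / 68.3% |
| 40% | 2.52 / 2.64 / 2.76 / 2.94 | 87.6 / 84.4 / 81.1 / 76.2% |
| 60% | 2.79 / 2.96 / 3.14 / 3.41 | 80.2 / 76.3 / 72.5 / 67.3% |

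Across control rates of 30-45%, power at OR 2.8 is 87-88% unclustered, 80-81% at DE 1.20 and 75-76% at DE 1.35.

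**8. Aim 2 arm-by-time test, unclustered** (test of within-woman slopes, 15,000 runs, m from 3 to 8). Type I error is 5.1-5.2% when the ICC of change is 0, 6.2-9.1% at 0.05 and 7.3-12.9% at 0.10.

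**9. Number of groups.** Section 3.0 allows 5-9 rounds per site, which gives at most 9 × 8 = 72 women against a target of 75, although recruitment is open-ended ("sessions at each participating site for three consecutive weeks until we reach our target population of 150 Latina women"). Reaching 75 takes about 10 groups of 8 (75/8 = 9.4) or 15 groups of 5 per arm. Section 6.2 implies 15 cohorts in all ("For cohorts 2-15, after the participant completes the final/third survey").

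**The case against.** **The size is assumed.** The documents give no group ICC. The same one or two health workers per site and six monthly individual booster calls before the outcome may keep the correlation low. If 100 women were analysed, as Phase 6a assumes under maximum attrition, groups would average 5 × 100/240 = 2.1 to 8 × 100/240 = 3.3. With 2 per group, type I error at ICC 0.05 is only 5.2-5.9%. This stands as a limit on size. The 100-woman case, however, belongs to Phase 6a, while the Phase 3 calculations use 150. The 15 cohorts point the other way: if each is one group, 150/15 = 10 completers per group, DE is 1 + 9 × 0.05 = 1.45 and alpha is about 10%.

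**OR 2.8 may have slack.** At control rates of 30-45% it tolerates a design effect of about 1.20. That is true, but the plan neither states the rate nor claims the allowance.

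**Phase 6a may be a special case.** Volunteering happens at shared events, and a mammogram is an individual act. The difference is reasonable, but the plan does not argue it, and the psychosocial outcomes of Aim 2 include norms and support.

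**The Aim 3 clustering clause might reach further**, since it refers to Phase 3 outcomes generally. It sits in the network paragraph and names peer referral only, so it cannot be relied on for Aims 1 and 2.

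**Arm is still one site.** A group term cannot separate site from intervention. This is correct, and it limits what the fix achieves.

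**Conclusion.** The concern holds. Aims 1 and 2 omit the unit in which the intervention is delivered, the sponsor's own rule for Phase 6a includes it, and every Phase 3 detectable effect is stated without a group allowance.

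The direction for Aim 1 is certain given any positive within-group correlation; the amount is not. It ranges from negligible at ICC 0.01 to a true error rate of up to 13.7% at ICC 0.10 with 8 analysed women per group. Aim 2 is affected only through correlated change. Whether OR 2.8 stays detectable depends on a control rate and an ICC that the plan does not give. This should be fixed before analysis: choosing whether to cluster after seeing the data would itself invite bias.

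**What to change.** - **Aim 1:** add a random intercept for delivery group, or use GEE clustered on group, with a small-sample correction and degrees of freedom based on the number of groups.
- **Aim 2:** add a group level with group-varying time effects. A group intercept alone does not protect the arm-by-time test. With 3-5 women per group the model may not converge, so name a fallback, such as group-robust standard errors.
- **Aim 3:** state that the delivery group counts as clustering.
- **Missing data:** include the group in the imputation model, so that imputation does not distort the within-group correlation.
- **Detectable effects:** restate them with a stated control rate and a range of group ICCs.
- **Groups:** reconcile the number and size of groups across sections 3.0, 6.2 and 6.4, so that the design effect can be set.
- **Limitation:** state that each arm is one site, so group clustering corrects the standard error only for variation between groups within a site.

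The cost is SAP wording, a group identifier in the analysis file, wider intervals, fewer degrees of freedom and less favourable detectable effects. The confounding of site with arm remains.

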3.0 Objectives/Aims

The primary goal of this proposed work is to develop materials and conduct a trial that would examine the relative efficacy of education and empowerment interventions to improve breast cancer screening among Chicago-based Latinas. With regard to our objectives, we proposed to:

Aim 1: Develop and compare the efficacy of a breast health empowerment intervention on guideline-concordant screening compared to an education intervention, using an area-level treatment control group design with a community-based sample of 150 Latinas. The empowerment arm will include breast health and empowerment information (e.g., how to begin conversations, where to volunteer). The education arm will include only breast health information. Content draws from my team's existing materials. Hypothesis: Empowerment participants will have increased screening compared to education participants.

Aim 2: Compare interventions' effects on psychosocial facilitators of screening across six months. Hypothesis: Empowerment participants will have sustained increases in self-reported self-efficacy, norms, support, and knowledge about breast cancer screening compared to education participants.

Aim 3: Compare interventions' network effects through egocentric network analysis. Hypothesis: Empowerment participants will have greater social connectedness related to breast health and network size and will have referred a greater number of peers to participate in the study compared to education participants.

Aim 4: Characterize intervention effects on family and friends of intervention participants.

Aim 5: a) Determine the incremental costs for each additional woman screened for the empowerment approach relative to the education approach, combining new cost data with existing effect measures in our trial. Hypothesis: The empowerment intervention will have low incremental costs for each additional woman screened, especially when including indirect effects. b) Use those data and published literature to compare approaches in terms of achieving HP2020 goals and costs for additional life-years gained across 10 years, using existing simulation platforms. Hypothesis: The empowerment intervention will be more cost-effective than the education intervention in terms of life years gained.

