5.0 Subject Enrollment

There will be a total of 300 participants enrolled in our study, including Phase 1 and 2 participants (40 Latinas, 15-30 community health workers), Phase 3 and 5 participants (240 Latinas who enroll, of which 150 estimated to complete entire study), and Phase 4 participants (20 family/friends).

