5.1 Recruitment

For Phase 3, we will recruit approximately 150 Latina women (75 at TRP and 75 at Juan Diego):

- Flyers will be posted at Centro Comunitario Juan Diego, The Resurrection Project and other community venues within target areas (Pilsen, Little Village, East Side and South Chicago,) and be distributed by electronic listservs in English and Spanish.
- Participants may also recruit their peers through sharing flyers/coupons and/or providing [name] contact information for screening. Participants will have the opportunity to take recruitment coupons throughout the three intervention sessions. They will be told that they can recruit other women until the third survey/they complete participation in the project. If they choose to take coupons, study staff will record which numbers belong to which participant via their participant id. The number of coupons given to each participant will depend on the participant's interest in distribution and how many they want. The study staff will record the total number each person obtains as well as the respective codes. When recruiting others, seed participants will provide individuals with coupons that have unique tracking codes. How many coupons are distributed and to whom will depend on the seed participants' interests and actions after they take the coupons from study staff. When interested individuals call, they will provide the unique tracking code on their coupon. After the call, the staff member will update the file that includes identifiable elements by inputting the coupon code. That said, no other information from the event will be kept in the database, including whether the individual agreed to be screened or ultimately participated.
- They will be compensated \$15 for each peer who contacts the study team, regardless of whether the peer is eligible and the extent to which they choose to undergo screening, consent, or participating in the intervention.
- Interested participants will call the PI, [name], or UIC staff [Appendix P], who will enter the name, address and phone number in a Call Log; screen women for eligibility; and obtain scheduling information.

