We will now work on implementing the intervention and assessing changes across interventions with regard to Aims 1-3 outcomes (screening, psychosocial facilitators, network effects). We plan on recruiting 150 Latina women to participate in the Intervention. 75 women will be recruited at The Resurrection Project and 75 women will be recruited from Centro Comunitario Juan Diego. No contact information on women who have participated in any previous focus groups or will we re-contact any woman who has already participated in a focus group for future trial. We will only invite new recruits for the intervention. We will be conducting educational classes and workshops at the two participating sites. The Intervention is broken down into 3 sessions at each site across 3 consecutive weeks. Each session will be held with 5-8 recruited participants. We will hold 5 – 9 sessions at each participating site for three consecutive weeks until we reach our target population of 150 Latina women. The variations in the implementation of Phase 3 Intervention will be the Workshops at each site. Besides each site conducting a Breast Cancer Education session at Session 1, TRP will conduct Communication and Volunteerism workshops at Session 1 and 2. Juan Diego will conduct Diet and Physical Activity workshops at Session 1 and 2. Our outcomes will be measured by Surveys assessed during Session 1, Session 3, and six months post-participation in workshops for 20-30 minutes. For participants were in Cohort 1 (who completed participation before approved consent addendum), they will be contacted by phone up to 3 times with a script including consent addendum information to be given that information, wherein they can elect to be notified about future studies, if they are interested. If they are not interested, their data will be eliminated from this file. For cohorts 2-15, after the participant completes the final/third survey, her data will be eliminated from this file, if she chooses not to be contacted for future studies. If she chooses to be contacted for future studies, her name and phone number (nothing else) will be kept and it will be recorded that she has completed participation, but is willing to be contacted in the future. Subsequently, each time she is contacted, this file will be updated to include a summary of the call. During each call, UIC staff will query the woman about her interest in being contacted in the

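### Phase 3 is described both as 150 women recruited and as 240 enrolled with 150 completing; the power statements fit only the second, and the total of 300 is below its own listed parts

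*Combined protocol and SAP*

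**What the plan says.** Two descriptions of Phase 3 stand together in the current text.

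- **150 recruited.** Section 5.1: "we will recruit approximately 150 Latina women (75 at TRP and 75 at Juan Diego". Sections 1.0, 3.0, 6.1 (Phase 3) and 6.4 give the same target, and the schedule table in Section 6.2 is headed by 75 women per site ("Juan Diego 75 Latina Women"). Section 6.4 holds sessions "until we reach our target population of 150 Latina women", Section 3.0 repeats that sentence, and Section 6.2 has "sessions at each participating site for three consecutive weeks until we reach the targeted 150 Latina women".
- **240 enrolled.** Section 5.0: "240 Latinas who enroll, of which 150 estimated to complete entire study". The same sentence is in Sections 3.0 and 6.4, so those two sections carry both descriptions. It is part of an itemised study total of 300.

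Aim 1 refers to a trial "with a community-based sample of 150 Latinas", which suits either description.

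The Phase 3 power statements (Sections 9.0 and 12.1) use 150 women, two-sided 0.05 and 80% power. They give OR 2.8 for screening (the "minimal detectable effect of study arm differences among 150 Latinas on screening") and Cohen's f² = 0.05 for network outcomes. Section 9.0 adds a small/medium arm-by-time interaction, based on 150 participants and 450 survey time points. None says whether 150 means enrolled or completing. No education-arm screening rate is given.

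**The concern.** In one description 150 is where recruitment ends. In the other it is what remains after 90 of 240 women are lost. Both cannot be the operating plan. The power statements need 150 women with outcome data, and 450 surveys is three from each of them. Recruitment that stops at 150 delivers this only if nobody is lost, and the plan elsewhere expects to lose more than a third.

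At stake is whether the stated sensitivity for Aims 1 to 3 describes the trial that will be run. Site staff following the sentences on sessions would stop at 150, while anyone following Section 5.0 would continue to 240.

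**Working it through.** **Inputs from the documents.** 150 recruited (Sections 5.1, 6.2, 6.4); 240 enrolled and 150 completing (Section 5.0); OR 2.8, f² = 0.05, two-sided 0.05, power 0.80 (Section 9.0). **Assumed:** an education-arm screening rate p0, scanned because none is stated; 1:1 allocation; no clustering or covariates.

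**1. Loss and surveys.** 1 − 150/240 = 37.5%. 150 × 3 surveys = 450, which fits 150 completing. Recruiting 150 with that loss gives 150 × 150/240 = 93.75, about 94 women.

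**2. The plan's OR 2.8 at N = 150.** With p1 = p0·OR/(1 − p0 + p0·OR), n per arm and p̄ the mean of p0 and p1:

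power = Φ{ [ |p1 − p0|·√n − 1.96·√(2p̄(1 − p̄)) ] / √(p0(1 − p0) + p1(1 − p1)) }

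At p0 = 0.20, p1 = 0.56/1.36 = 0.412. With n = 75, the numerator is 0.212 × 8.660 − 1.277 = 0.557 and the denominator is 0.634. Then Φ(0.878) = 0.81. Across p0:

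| p0 | N = 94 | N = 150 | N = 240 |
|---|---|---|---|
| 0.10 | 0.43 | 0.61 | 0.82 |
| 0.20 | 0.61 | 0.81 | 0.95 |
| 0.40 | 0.69 | 0.88 | 0.98 |
| 0.60 | 0.60 | 0.80 | 0.95 |
| 0.70 | 0.50 | 0.71 | 0.89 |

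At N = 150, power reaches 0.80 for p0 from about 0.19 to 0.60. The detectable OR is 2.77 at p0 = 0.20 and 2.79 at 0.60, so 2.8 is a credible figure for 150 analysed. At N = 94 the maximum over p0 from 0.02 to 0.90 is 0.69.

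**3. The plan's f² = 0.05.** Noncentral F with one tested predictor and λ = f²·N. At N = 150 the detectable f² is 0.053 (power 0.78 for 0.05), consistent with the plan after rounding. At N = 94 the detectable f² is 0.085 and power for 0.05 is 0.57.

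**4. Interaction.** Not recomputed, because the effect metric is not stated.

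**5. Groups.** Section 3.0: "Each session will be held with 5-8 recruited participants". With 5 to 9 at each of two sites, the range is 5 × 5 × 2 = 50 to 9 × 8 × 2 = 144 women. Enrolling 240 would need at least 240/8 = 30 groups.

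**6. Total.** The parts listed in Section 5.0 are 40 + (15 to 30) + 240 + 20 = 315 to 330. With 150 in place of 240 the sum is 225 to 240. Leaving out the health workers, 40 + 240 + 20 = 300 exactly. The health-worker count is itself 15–30 in Sections 3.0, 5.0, 6.2 and 6.4, but 20–30 in Section 6.1 and, as 10–15 in each of two phases, elsewhere in Section 3.0.

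**The case against.** The strongest answer is that one reading is coherent: 240 enrol, 150 complete, and the power statements use the 150. Loss is then already allowed for, and the 450 surveys and the detectable effects follow. That stands. What remains against it is the recruitment text, which sets 150 as the target and the end point.

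Four stronger readings are tempting, and the documents do not support them.

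- **That the trial is underpowered, with about 94 completing.** This joins a recruitment figure from one description to a loss rate from the other, and no passage combines them. It shows what the ambiguity could cost. It is not a forecast. The opposite case also needs stating: Section 9.0 plans multiple imputation, and if all 240 contributed full information, power for OR 2.8 would be 0.82 to 0.98 over control rates of 10% to 70%. That is an upper bound, because imputation does not recover outcomes that were never observed.
- **That Phase 6a contradicts the 150.** Its 100 women are labelled a maximum-attrition case. From 240 that is a 58% worst-case loss, which does not conflict with an expected 37.5%. A larger detectable effect at 100 than at 150 is also what one would expect.
- **That 300 is unrelated to either description.** It equals the 240 version without the health workers, so their omission is the likely source. The sentence nevertheless lists them as included.
- **That the group count caps Phase 3 at 144.** Sessions continue until 150 is reached, and the text also mentions cohorts up to 15. The group range sits badly with 240 but says little against 150.

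**Conclusion.** The contradiction is in current text and affects a figure that the analysis relies on. The power statements agree with 150 completing out of 240 and disagree with recruitment that ends at 150. No power figure is shown to be wrong if 150 women are analysed: OR 2.8 then has at least 80% power for control rates of about 19% to 60%, and f² = 0.05 is right to rounding. In the hypothetical case of 150 recruited with 37.5% lost, power for OR 2.8 would be at most 0.69, and power for f² = 0.05 would be 0.57. These results rest on an assumed control rate, equal arms, and no clustering or covariates. The total of 300 is an addition error of 15 to 30 people against its own list. It and the health-worker range are clerical and do not affect power. The point should be fixed.

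**What to change.** No participants need to be added to either description.

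1. State one Phase 3 enrolment target and one expected six-month N. Make the recruitment targets, the sentences on when sessions end, and the groups per site agree with them in Sections 1.0, 3.0, 5.0, 5.1, 6.1, 6.2 and 6.4.
2. If 240 is the enrolment target, keep the power statements, label 150 as the number completing, and correct the total to 315–330 (320–330 with 20–30 health workers).
3. If 150 is the enrolment target, restate the detectable OR, interaction and f² at the expected six-month N, with the assumed education-arm screening rate. Correct the total to 225–240 (230–240 with 20–30 health workers).

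The cost is text edits, including Sections 9.0 and 12.1. Under the third option the stated sensitivity may become less favourable.
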